The coverage and capabilities that will distinguish the FoodImage app from the SmartIntake® app will include:

- A. **Comprehensive measurement of food waste.** The FoodImage app will quantify food waste at all stages where food waste occurs at the consumer level (e.g., left-overs after a meal, cabinet or refrigerator/freezer purges, food preparation, etc.). The existing SmartIntake® app quantifies *plate* waste that is present at the end of meals and this is used to calculate food intake (food intake = food selection minus plate waste). SmartIntake® does not, however, determine if the plate waste was discarded, saved to eat later, etc., thus, it cannot determine if *plate* waste is *food* waste.
- B. **Receipt scanning capability.** An exploratory module will be developed in which receipts from food purchases are scanned. This will provide the potential to calculate the dollar value loss of waste using prices actually paid by the participant. While this module is exploratory and not primary, it holds promise for assessing the exact purchase value of food waste and for exploring hypotheses that link food acquisition price to eventual food consumption and food waste.

Phase I (Overview)

Phase I of this study will consist of testing the FoodImage App with participants in a lab setting. The primary purpose of Phase I will be to test the measurement features of the FoodImage app under controlled conditions and to obtain user satisfaction data about the app. Participants will use three methods in the lab setting:

- 1) the FoodImage app,
- 2) a pen-and-paper record, where the participant will visually estimate portion sizes, and
- 3) a pen-and-paper record, where the participant will use a kitchen scale to weigh the foods.

Participants will be randomly assigned to the order in which these methods will be used, as described below. It is noted that, by necessity, the last method that will be used is a pen-and-paper record with a kitchen scale since this procedure will cue participants to the actual weight of the foods and corrupt their visual estimates, should the visual estimation procedure occur after the method that relies on a kitchen scale. Thus, the order in which participants first use FoodImage vs. a pen-and-paper record with visual estimates of portion size will be counterbalanced. The two orders that will be balanced among participants are:

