- 1) FoodImage, pen-and-paper records with visually estimated portion size, then pen-and-paper records with the ability to use a kitchen scale.
- 2) Pen-and-paper records with visually estimated portion size, FoodImage, then pen-and-paper records with the ability to use a kitchen scale.

Accuracy will be evaluated for both the FoodImage app and the two methods that rely on pen-and-paper records by comparing estimated food waste from these three methods to directly weighed food waste. Participants will use these three methods to estimate the amount of:

- 1) food waste that is generated when they prepare provided foods,
- 2) the resulting food portions that represents the amount of served food during a simulated meal, and
- 3) the amount of food that remains (plate waste) after the study staff discards a randomly selected amount of the served foods (participants will not eat any food).

Participants will also use all three methods to document foods from a simulated shopping trip, where participants will be provided with a grocery bag(s) of foods products and one or more receipts. It is recognized that some food products may not require use of the kitchen scale since

the packaging contains the weight or portion size of many foods. Finally, participants will also use all three methods to document foods that are to be discarded from a simulated kitchen clean out. To simulate the kitchen clean out, study staff will present to the participant a series of food products on a counter and participants will be asked to document what and how much food would be thrown away (the foods will not actually be discarded). The training materials that will be used to teach participants how to use the pen-and-paper records and FoodImage app are included in Appendix A.

Following the laboratory-procedures described above, participants in Phase I will complete questionnaires assessing their satisfaction with the FoodImage app, if they prefer to use the FoodImage app vs. a pen-and-paper record, etc. (these questionnaires are detailed below).

Phase II (Overview)

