- *User Satisfaction Survey*- This survey asks questions to help staff understand participants' satisfaction with using an iPhone app (FoodImage) to take and send photos of food waste (Appendix B.2.c).

- *Food Environment Questionnaire*- This questionnaire asks questions about purchasing food for the household (Appendix B.2.d).
- *Waste Toss Methods Questionnaire*- This questionnaire asks questions about how participants typically dispose of food in their household (Appendix B.2.e).
- *Food Waste Tip Questionnaire* – This questionnaire asks questions to help staff understand participants' satisfaction with receiving training tips to help reduce food waste (Appendix B.3.a).

Data Analysis and Specimen Management

Phase I analysis objectives include:

- 1) Determining if food waste measured with the FoodImage app is equivalent to the criterion value (directly weighed food waste) for each source (plate waste, food purges, etc.). Error (the difference between food waste measured with the FoodImage app and the criterion value) will also be quantified for each source.
- 2) Determining if food waste measured with each of the pen-and-paper diary methods (with and without a kitchen scale) is equivalent to the criterion value for each source. Error will also be quantified for each source.
- 3) Determining if the error from the FoodImage app is smaller than error from the pen-and-paper records.
- 4) Determining if satisfaction ratings differ significantly between the app and the pen-and-paper record approaches.
- 5) Determining if the amount of time respondents took to complete measurements differed between the app and diary approaches.
- 6) Qualitative assessments by respondents of the desirable and undesirable features of the app and pen-and-paper records.
- 7) Determining if the variance of waste measures differed between the app and pen-and-paper record approaches.
- 8) Assessing the accuracy of receipt data as captured by participants using the app.

Power Analysis. We base our power analysis on plate waste data gathered from previous research conducted at PBRC [20]. With an N of 24, we are powered to detect equivalence within 20 grams with power of 0.80 and alpha of 0.05. Also, *t*-tests to determine if the error from the app (weighed food waste minus estimated waste) differs significantly from the error from the diary method is powered to detect differences as small as 12.8 grams.

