It is hypothesized that food waste will be equivalent (within 20 grams) when measured with the app vs. direct weights of food waste, while food waste measured with the diary method will not be equivalent to directly weighed food waste. It is also hypothesized that the error from the app will be significantly smaller than error from the diary method.

Phase II analysis objectives include:

- 1) Quantifying baseline distributions for total weight of household food waste

- 2) Determining the effectiveness of the behavioral nudge in altering
 - a) Total daily weight of household food waste,
 - b) Total daily weight of each source of household food waste by occasion, including
 - i) plate waste,
 - ii) food prep waste,
 - iii) purge waste,
 - c) Total daily weight of each source of food waste by food type (e.g., dairy, meat, fruits, etc.) and by macronutrient,
 - d) Daily percent of served food that is wasted, and
 - e) Total amount of food purchased by weight and value.
- 3) Quantifying satisfaction levels with the FoodImage app as measured in Appendix B.1.a. (User Preference Survey) and Appendix B.2.c (User Satisfaction Survey),
- 4) The demographic, household and attitudinal factors measured in Appendix B.2.d (Food Environment Questionnaire) related to
 - a) Effectiveness of the behavioral nudge intervention in reducing food waste generated and all subcomponents listed above, and
 - b) Satisfaction levels with the app as measured in Appendix B.2.c (User Satisfaction Survey).

Withdrawal of Subjects

Subjects may be withdrawn from the study if they are non-compliant with study procedures and they will be notified of their withdrawal via telephone or mail. Subjects may voluntarily withdraw from the study at any time. No additional data will be collected and they will be considered drop outs in the study.

Risks to Subjects

This study involves no greater than minimal risk. The main risk is breach of confidentiality, and the PBRC team will work to minimize this during data collection, handling, and analysis.

Potential Benefits to Subjects

Participants may benefit by increased awareness of their food waste behaviors.

Setting

All research procedures will be conducted at PBRC and in participants' natural environment.

Resources Available

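### The only app-versus-diary error test described for Phase I uses signed error, so by itself it compares mean bias and cannot show that app error is smaller

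*Combined protocol and SAP*

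**What the plan says.** All references are to the combined protocol and SAP.

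- **Objective 3** (Data Analysis and Specimen Management, Phase I objectives): "Determining if the error from the FoodImage app is smaller than error from the pen-and-paper records".
- **Hypothesis** (after the Power Analysis): "It is also hypothesized that the error from the app will be significantly smaller than error from the diary method".
- **The test** (Power Analysis): t-tests "to determine if the error from the app (weighed food waste minus estimated waste) differs significantly from the error from the diary method", with a stated detectable difference of 12.8 g. Pairing, sidedness and power are not restated for this figure.
- **Definition of error** (objective 1): "Error (the difference between food waste measured with the FoodImage app and the criterion value) will also be quantified for each source". This too is a plain difference. Absolute or squared error appears nowhere.
- **Equivalence** (Power Analysis, N = 24): "we are powered to detect equivalence within 20 grams with power of 0.80 and alpha of 0.05". Objectives 1 and 2 apply it to each method against weighed waste, by source.
- **Variance** (objective 7): "Determining if the variance of waste measures differed between the app and pen-and-paper record approaches". No test is named.
- **Design** (Phase I Overview): "Accuracy will be evaluated for both the FoodImage app and the two methods that rely on pen-and-paper records". Every participant uses all three methods. The kitchen scale comes last because "this procedure will cue participants to the actual weight of the foods and corrupt their visual estimates", which implies that the same foods are measured by each method.

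**The concern.** Smaller error is a statement about size. The described test takes the mean of a signed quantity, in which a 40 g overestimate and a 40 g underestimate average to zero. If the same foods are measured by both methods, the weighed value also cancels in the within-person contrast, leaving the difference between the two mean estimates.

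Three misreadings become possible. A real gain in precision can be missed, a difference can be declared between equally accurate methods, and a significant result can arise when the app is the less accurate method. On a signed scale, the method that overestimates more also has the numerically smaller error.

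Comparing the accuracy of the app and the diary is specific objective 2 of the study. The opening statement of goals lists reduced bias and reduced measurement error separately; a signed contrast addresses only the first.

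**Working it through.** **Inputs from the documents:** N = 24, equivalence margin 20 g, power 0.80 and alpha 0.05 (stated for equivalence), detectable difference 12.8 g. No error SD is given.

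**The plan's figure.** Without an SD, 12.8 g cannot be reproduced, only inverted. Assume 80% power and alpha 0.05 (noncentral t):
- paired, two-sided: detectable difference = 0.597 × SD, so SD = 12.8 / 0.597 = 21.4 g
- paired, one-sided: 12.8 / 0.523 = 24.5 g
- two groups of 24, two-sided: 12.8 / 0.826 = 15.5 g

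Two one-sided equivalence tests with a 20 g margin, zero bias and 80% power allow an error SD of 32.5 g at 0.05 per side, or about 29 g at 0.025. The two SDs may describe different quantities, so the gap between them is not itself an error.

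**Simulation.** 40,000 replicates, n = 24, bivariate normal errors, paired two-sided t-tests at 0.05. Error is weighed minus estimated, so a negative bias means overestimation. Biases, SDs and correlations are assumptions, chosen to keep the paired-difference SD near 21.4 g. For example, √(9.6² + 19.2²) = 21.5 and √(12.4² + 24.7² − 12.4 × 24.7) = 21.4.

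| Case (app / diary) | Signed test significant | Absolute-error test |
|---|---|---|
| Unbiased; SD 9.6 / 19.2 g; correlation 0 | 5% | favours app 83% |
| Unbiased; SD 12.4 / 24.7 g; correlation 0.5 | 5% | favours app 90% |
| Unbiased; SD ratio 1.5; correlation 0 or 0.5 | 5% | favours app 40–48% |
| Bias -6.4 / +6.4 g; SD about 15 g each; correlation 0 | 80% | 5% (equally accurate) |
| Bias -12.8 / 0 g; SD 15.1 g each; correlation 0 | 80% | favours diary 25% |
| Bias 0 / 12.8 g; SD 15.1 g each; correlation 0 | 80% | favours app 25% |
| Bias 0 / 12.8 g; SD 21.4 g each; correlation 0.5 | 80% | favours app 11% |
| Bias 5 / 20 g; SD 15 g each; correlation 0 | 91% | favours app 71% |

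Rows 1–5 show the defect. Rows 6–8 show where signed error does better. The reason is the mean absolute error of a normal variable, σ√(2/π)·exp(−μ²/2σ²) + μ(2Φ(μ/σ) − 1). With σ = 15.1 it is 12.0 g at μ = 0 and 16.1 g at μ = 12.8. A 12.8 g difference in bias is therefore only 16.1 − 12.0 = 4.1 g in mean absolute error.

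**Do the other analyses fill the gap?**
- *Equivalence.* In rows 1 and 2 both methods pass in 99.9% and 97% of replicates, so equivalence does not separate them. With larger spread it separates them in part: app SD 32.5 g and diary SD 40 or 45 g (correlation 0.85 or 0.90), the app alone passes 29% or 44%.
- *Objective 7*, taken as a paired (Pitman-Morgan) variance test on the waste measures in rows 1 and 2. It favours the app 90–96% with no true variation in waste, 60–84% at a true SD of 10 g, 27–54% at 20 g and 11–22% at 40 g. Plate waste does vary, because staff discard a random amount.

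**The case against.** The strongest reply is that the signed formula is a parenthesis in a power paragraph, not an analysis specification, and that the investigators may have meant absolute error for objective 3. That is possible, but no passage says so. A reader might infer that the investigators deliberately chose the wrong metric. The documents do not support that. They show a directional question with no stated metric, and one described test whose metric does not match it.

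Second, the plan expects the app to be equivalent to weighed waste and the diary not to be. If the diary fails through bias, the signed test works well: app bias 0, diary bias 20 g, SD 21.4 g each and correlation 0.5 give 99% power against 37% for absolute error, and the app alone passes equivalence 95%. This stands, and it is the reason to keep the signed test. But a method can also fail equivalence through spread. An unbiased diary with SD 45 g passes only 36% of the time, and against an unbiased app the signed test still rejects at 5%.

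Third, the signed errors are to be quantified by source, so opposite biases would be visible in the means. Objective 7 also addresses spread. Both are real safeguards, and a reader who infers that the plan is blind to precision goes too far. Neither compares size of error between methods. Nor do the documents say that the clean-out products differ between participants, so dilution of objective 7 by true variation should not be claimed for that source.

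Finally, the magnitudes are conditional. The text says only t-tests, the SDs lie in a cited source, and the 32.5 g cases need high correlations. This stands. The 5% rejection rate under equal biases does not depend on the chosen SDs or correlation; the other percentages do.

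**Conclusion.** The point holds in this form: the one app-versus-diary error test described is a contrast of mean bias, and by itself it cannot establish that app error is smaller. It rejects only at its 5% type I rate when both methods are unbiased and the app is more precise. It can be significant (80% in the cases shown) when the methods are equally accurate or the app is worse. The equivalence tests, the reported signed errors and objective 7 narrow the gap without closing it.

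The percentages are illustrations. They assume normal errors, a paired two-sided test, 80% power carried over to the 12.8 g figure, and chosen biases, SDs and correlations.

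A reader might go on to infer that the signed test should be replaced, or that 12.8 g is wrong. Neither follows. The signed test is the more powerful one when methods differ mainly in bias, and 12.8 g cannot be checked without an SD. The issue should be fixed before analysis; it does not affect data collection.

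**What to change.** - For objective 3, add a paired comparison of absolute error, |estimated − weighed|, per participant and source. Compare the app with each pen-and-paper method separately (visual estimate; kitchen scale), since the diary in the hypothesis could mean either. Base the smaller-error conclusion on this comparison.
- Keep the signed-error t-test as a tested comparison of bias, and attach the 12.8 g figure to that test only. State its pairing, sidedness and power.
- State a separate detectable difference for absolute error, derived from the prior plate-waste data.
- For objective 7, compare the variance of the errors (estimated minus weighed) rather than of the waste measures, so that true variation in waste does not dilute it.

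The cost is some extra analysis and a less favourable power statement. No new data are needed, because weighed and estimated values are already collected for every method. The absolute-error test may be underpowered at N = 24 if the methods differ mainly in bias, and the plan should say so.

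### The plan predicts that the diary will not be equivalent to weighed waste, but the only planned diary-versus-weighed inference can show equivalence or fail to show it

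*Combined protocol and SAP*

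**What the plan says.** All of this stands under Data Analysis and Specimen Management.

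- **Phase I objective 2** plans "Determining if food waste measured with each of the pen-and-paper diary methods (with and without a kitchen scale) is equivalent to the criterion value", by source, and adds "Error will also be quantified for each source".
- **Power Analysis**: with N = 24 the study is "powered to detect equivalence within 20 grams with power of 0.80 and alpha of 0.05". No equivalence procedure is named, no SD is given, and the text does not say whether 0.05 is per side. A t-test is also powered, for differences down to 12.8 g, to determine whether "the error from the app (weighed food waste minus estimated waste) differs significantly from the error from the diary method".
- **Hypotheses after the power paragraph**: for the app, the prediction is that "food waste will be equivalent (within 20 grams) when measured with the app vs. direct weights of food waste". For the diary, the same sentence predicts the opposite: "while food waste measured with the diary method will not be equivalent to directly weighed food waste". A further hypothesis is that app error will be significantly smaller than diary error.
- **Objectives 3 and 7** compare methods with each other: "Determining if the error from the FoodImage app is smaller than error from the pen-and-paper records" and "Determining if the variance of waste measures differed between the app and pen-and-paper record approaches".

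Objective 2 covers two diaries, with and without a scale. The hypothesis speaks of one diary method and does not say which.

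**The concern.** An equivalence test has non-equivalence as its null hypothesis. Rejecting the null supports equivalence. Not rejecting it leaves two explanations open: the diary's mean error may lie outside the margin, or it may lie inside and be estimated too imprecisely to show it. The prediction that the diary is *not* equivalent is a claim about the first, and the planned determination cannot separate the two.

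Objectives 3 and 7 do not fill the gap, because neither sets a diary against weighed waste. The error summary in objective 2 describes the diary but does not decide when the prediction is supported.

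At stake is one of the study's headline contrasts. If a failed test were read as support, a diary with no mean error could appear to confirm the prediction through noise alone. A related gap affects the claim of smaller app error: the power paragraph defines error with its sign, so a t-test on it compares mean bias and does not by itself show which method has the smaller error.

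**Working it through.** **Inputs from the documents:** N = 24, margin 20 g, power 0.80, alpha 0.05, detectable difference 12.8 g. **Assumed:** symmetric margin, two one-sided tests (TOST) on the paired error, normally distributed errors, the same 20 g for the diaries.

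**1. The plan's own figure.** Without an SD, the 0.80 cannot be reproduced forwards, so the SD is back-solved. TOST passes when |mean error| + t × s/√24 < 20, with t = 1.714 (0.05 per side, 23 df). Power is computed exactly over the distribution of the sample SD. Power 0.80 at zero bias requires SD = 32.5 g. Rough check: SE = 32.5/4.899 = 6.63 g and half-width 1.714 × 6.63 = 11.4 g, so the mean must fall within ±8.6 g. Then P(|Z| < 8.6/6.63 = 1.30) ≈ 0.81, against 0.80 exactly.

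Other readings: 0.025 per side gives SD 28.9 g; power planned at a 5 g bias gives 28.4 g. A low value of 21.4 g is the paired SD implied by 12.8 g at an assumed 80% power and two-sided 0.05. That is the SD of app error minus diary error, a different quantity, and serves only as an assumed low case.

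**2. How often a diary inside the margin fails, per source**

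| SD, alpha per side | Bias 0 g | 5 g | 10 g |
|---|---|---|---|
| 32.5 g, 0.05 | 20% | 31% | 57% |
| 28.9 g, 0.025 | 20% | 34% | 63% |
| 28.4 g, 0.05 | 9% | 20% | 49% |
| 21.4 g, 0.05 | 0.5% | 5% | 28% |

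The 20% entries at zero bias are simply 1 − 0.80. A noisier diary fails more often: at zero bias and 0.05 per side, 46% at SD 40 g and 78% at SD 50 g.

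**3. A rule that separates the outcomes.** Call a diary *equivalent* if the confidence interval of mean error lies wholly inside ±20 g, *not equivalent* if wholly outside, and *inconclusive* otherwise. In every case in the table, the interval lies wholly outside in at most 0.1% of trials. For diaries truly outside the margin (90% interval):

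| True bias | SD 32.5 g: shown not equivalent / inconclusive | SD 21.4 g: shown not equivalent / inconclusive |
|---|---|---|
| 25 g | 18% / 81% | 30% / 70% |
| 30 g | 43% / 57% | 72% / 28% |
| 40 g | 90% / 10% | 99.7% / 0.3% |

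**4. Signed error.** Take two methods with biases +10 g and −10 g and SD 32.5 g each. Their accuracy is the same, but their mean signed errors differ by 20 g. Simulated with N = 24, the two-sided paired t-test on signed error is significant in 53% of trials if the errors are independent, and in 99% if the SD of their difference is 21.4 g. On absolute error the same test is significant in 5%, its nominal rate.

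**The case against.** The harm depends on a reading that the sponsor has not adopted. Objective 2 is worded neutrally, and the planned error summary would expose a diary with near-zero mean error and wide spread. The app-versus-diary comparison is planned and powered separately. All rates rest on an assumed SD and run from 0.5% to 63% in the first table, and the leading 20% is the complement of the stated power.

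Much of this stands. A reader might infer that the plan will treat a failed equivalence test as confirmation; the documents do not say so, they only leave it open. A reader might also infer that the diaries have no margin. That goes too far: the app and diary predictions share one sentence, the power sentence is not restricted to the app, and a common 20 g is the natural reading. It needs stating, no more. Nor do the documents rank the Phase I hypotheses, so the point cannot be set aside as concerning a secondary one.

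What does not stand is that the error summary or the app-versus-diary test closes the gap. The first is descriptive and the second answers another question.

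**Conclusion.** The point holds as a mismatch between a stated prediction and the only inference planned for it. That conclusion comes from the text and does not depend on any SD. The size is illustrative: under TOST at 0.05 per side, N = 24 and a 20 g margin, an unbiased diary fails about 20% of the time per source at 32.5 g and about 0.5% at 21.4 g. Neither figure forecasts this trial.

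The documents do not support a wider reading in which the app equivalence test, the sample size, data collection or Phase II is undermined; none depends on the diary prediction. The signed-error point is narrower still: the t-test is a valid comparison of bias, but by itself it cannot carry the claim of smaller error. The plan should be corrected before analysis.

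**What to change.** 1. Name the equivalence procedure and the per-side alpha, and state that 20 g applies to both diaries.
2. Say which diary or diaries the hypothesis covers.
3. For each diary and source, apply the three-outcome rule above, using the interval that matches the chosen alpha (90% if 0.05 per side, 95% if 0.025). Report the hypothesis source by source, without a single overall confirmation. Alternatively, reword it to say that equivalence will not be demonstrated, which gives up any claim of shown non-equivalence.
4. For the claim that app error is significantly smaller, run the paired comparison on absolute error. Keep the signed comparison as a report of bias, and note that the 12.8 g detectable difference refers to signed error.

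Design, N and data collection do not change. The cost of the three-outcome rule is that some diary results will be inconclusive: 57% at a true 30 g bias with SD 32.5 g. The documents give no power for the absolute-error comparison, so it should be reported with its confidence interval.
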